8.1.1.3 Radiation Exposure from CTA Imaging, Including Rules for Repeating CTA Scans

The overarching principle for CTA imaging will be to maximize high-quality CTA imaging for endpoint ascertainment while minimizing radiation exposure to participants.

The anticipated median (range) radiation exposure per CTA imaging time point is 6 (3-10) mSv. A maximum cumulative radiation exposure of 30 mSv is anticipated in this study and will be monitored by the CTA core laboratory through a radiation monitoring escalation plan. Radiation dose will be estimated based on dose length product using a K (conversion) factor of 0.014. Dose-saving image acquisition techniques will be used where applicable.

The baseline and follow-up CTA scans may be repeated under certain circumstances.

In order to ensure that the overall radiation exposure remains within the specified limit, rules for CTA scans are detailed by time point below:

- 1 Baseline CTA (Day -30 to -1; Visit 2):
 - (a) If the baseline CTA scan is obtained but randomization does not occur within the prespecified screening window, there is a 30-day window to repeat screening and proceed with randomization using the initial baseline CTA. If repeat screening

extends beyond 30 days from date of initial baseline CTA scan, discussion with the Medical Monitor is required to determine whether the initial baseline CTA needs to be repeated before randomization.

- (b) If the baseline CTA scan is deemed uninterpretable by the core laboratory, it may only be repeated if corrective action can be taken to result in an anticipated total cumulative research radiation exposure of < 30 mSv for all CTAs.

2 End of study CTA (Day 253; Visit 13)

- (a) End of study CTA scan should not be performed in participants whose anticipated cumulative research radiation exposure would exceed 30 mSv.
- (b) If the end of study CTA scan is deemed uninterpretable by the core laboratory, it may only be repeated if corrective action can be taken to result in an anticipated total cumulative research radiation exposure of < 30 mSv.

For all repeat CTA scans:

- The eGFR must be re-measured before the CTA scan is repeated.
- The repeat CTA scan must be taken \geq 48 hours after the original CTA scan, and within the relevant study visit window.

8.1.1.4 CTA Image Analysis

Imaging personnel and equipment will undergo certification by a separate, independent, core laboratory that is blinded to study treatment. CTA imaging will be performed at time points as specified in the SoA. CTA coverage will extend from the right pulmonary artery to the diaphragm, to cover the full extent of the heart and coronary arteries.

Planned measurements include:

- NCPV_{MD}
- NCPV (global)
- LAPV
- CCI
[REDACTED]
- Any additional measurements as described in the CTA imaging manual/protocol

Critical alert findings of clinical importance will be interpreted locally and provided to the investigator to permit appropriate assessment and treatment. A full coronary CTA interpretation will not be performed locally.

The CTA images will be analyzed in the core laboratory. The CTA imaging manual describes the CTA imaging protocol, which will accommodate differences in imaging platforms across sites.

8.1.2 Echocardiography

Participants must meet the study eligibility criteria (Sections [5.1](#) and [5.2](#)) before undergoing echocardiogram imaging. If echocardiogram and CTA imaging are performed on the same day, echocardiogram imaging must always occur before CTA imaging, and before any additional beta-blocker is administered above the daily dose used by the participant.

Imaging personnel and equipment will undergo certification by a separate, blinded, independent core laboratory. Echocardiography will be performed at time points specified in the SoA (Section [1.3](#)).

Planned measurements include, as follows:

- Left Ventricular Ejection Fraction
- Left Ventricular GLS
- CCI
[REDACTED]
- Any additional measurements as described in the echo imaging manual/protocol

The echocardiogram images will be analyzed in the core laboratory. The echocardiography imaging manual describes the imaging protocol, which will accommodate differences in imaging platforms across sites.

If for any reason an echocardiogram image is deemed uninterpretable for any planned measurements by the core laboratory, then echocardiography may be repeated at the discretion of the investigator, participant, and Medical Monitor. The repeat echocardiogram must be obtained within the time specified for the visit window in the SoA (Section [1.3](#)).

8.2 Safety Assessments

Planned time points for all safety assessments are provided in the SoA (Section [1.3](#)).

8.2.1 Physical Examinations

A complete physical examination will be performed and will include assessments of the following: general appearance; the respiratory, CV, thyroid, muscular-skeletal (including spine and extremities) and neurological systems; the abdomen, skin, head and neck (including ears, eyes, nose and throat), and lymph nodes; weight and height.

An abbreviated physical examination will include, at a minimum, assessments of the skin, the respiratory and CV systems, the abdomen (liver and spleen), and any type of bleeding.

Physical examination will be performed at timelines as specified in the SoA (Section 1.3).

8.2.2 Vital Signs

Vital signs (BP and heart rate) will be measured at the time points specified in the SoA (Section 1.3). Measurements will be taken after the patient has rested for at least 5 minutes in a sitting position. If multiple vital signs measurements are taken, the last measurement is the one that should be recorded.

8.2.3 Electrocardiogram

Electrocardiogram will be performed at the time points specified in the SoA (Section 1.3).

Participants will have 12-lead ECG recordings taken as specified in SoA, recorded after a 5-minute rest with the participant in the supine position. Analysis of the ECG results will be performed locally and results recorded using electronic data capture.

8.2.4 Clinical Safety Laboratory Assessments

Blood samples for determination of clinical chemistry, hematology, and coagulation variables will be collected at the visits indicated in the SoA (Section 1.3).

Additional safety samples may be collected if clinically indicated at the discretion of the investigator. The date, time of collection, and type of sample will be recorded on the appropriate eCRF.

The clinical chemistry and hematology safety laboratory samples will be analyzed at a central core laboratory. Laboratory safety variables are listed in Table 10.

Table 10 **Laboratory Safety Variables**

Hematology (whole blood)	Clinical chemistry (serum)	Eligibility
B-Hemoglobin	S/P-Creatinine	Luteinizing Hormone
B-Leukocyte count	S/P-Bilirubin, total	Follicle Stimulating Hormone
B-Leukocyte differential count (absolute count)	S/P-ALP	HIV
B-Platelet count	S/P-AST	Hepatitis B
Coagulation panel including INR, and aPTT (screening only)	S/P-ALT	Hepatitis C
	S/P-Albumin	

	S/P-Potassium	
	S/P-Calcium, total	
	S/P-Sodium	
	S/P-CK	

If a participant shows an AST **or** ALT $\geq 3 \times$ ULN together with TBL $\geq 2 \times$ ULN refer to [Appendix E](#).
ALP, alkaline phosphatase; ALT, alanine aminotransferase; aPTT, activated partial thromboplastin time; AST, aspartate aminotransferase; CK, creatine kinase; HIV, human immunodeficiency virus; INR, international normalized ratio; S/P, serum/plasma; TBL, total bilirubin; ULN, upper limit of normal

8.2.5 Other Safety Assessments

8.2.5.1 Bleeding

Study participants will be monitored for AEs related to bleeding by reviewing AEs and SAEs assessed at time points specified in the SoA (Section 1.3). All bleeding events will be reported as AEs and characterized further, allowing for their classification according to bleeding type.

8.2.5.2 Monitoring for Hypersensitivity Reactions

Participants will be closely monitored during and after administration of study intervention during the observation period as specified in the SoA (Section 1.3) for hypersensitivity reactions, including monitoring for signs and symptoms of immune complex disease. Severe hypersensitivity reactions should be managed according to standard clinical practice, and medical equipment and staff trained to treat acute anaphylactic reactions must be available at all sites. If a hypersensitivity reaction occurs, dosing of the participant will be stopped.

Hypersensitivity reactions will be recorded as AEs or SAEs, as appropriate.

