2.3 Benefit/Risk Assessment

2.3.1 Risk Assessment

Table 6 Risk Assessment

Potential Risk of Clinical Significance	Summary of Data and/or Rationale for Risk	Mitigation Strategy
Study intervention		
Bleeding	
• CCI [REDACTED]• Activated platelets express CCI [REDACTED] and the IgG Fc receptor Fc_YRIIa. There is a hypothetical risk that crosslinking of platelets via Fc receptors could trigger platelet destruction leading to thrombocytopenia (Arman and Krauel 2015), which is a risk factor for bleeding.• There have been no indications of abnormal bleeding in monkeys during toxicity studies with MEDI6570. CCI [REDACTED]	
• Exclusion of participants with a history or presence of known bleeding disorder, active bleeding, or high risk of bleeding, need for chronic anticoagulant therapy or platelet count < 100000 platelets/μL. (Arman and Krauel 2015). Please refer to exclusion criteria (Section 5.2).• Standard hematological safety monitoring, including platelet count (Section 8.2.4), and monitoring participants for bleeding events (Section 8.2.5.1)• Encourage the use of PPIs if the concomitant use of NSAID therapy is required.• All bleeding events will be reported as AEs and characterized further.

Table 6 Risk Assessment

Potential Risk of Clinical Significance	Summary of Data and/or Rationale for Risk	Mitigation Strategy
Hypersensitivity reactions including anaphylactic reactions and immune complex disease	
 Pharmacological administration of any peptide or protein may lead to hypersensitivity reactions including anaphylactic reactions, and of most concern clinically, immune complex disease. CCl [REDACTED] 	
 Exclusion of participants with a known history of hypersensitivity reactions to other biologics, to human IgG preparations, or to any component of MEDI6570 (Section 5.2). Participants will be monitored closely during and after administration of study intervention for hypersensitivity reactions, including monitoring for signs and symptoms of immune complex disease. Severe hypersensitivity reactions should be managed according to standard clinical practice, and medical equipment and staff trained to treat acute anaphylactic reactions must be available at all sites (Section 8.2.5.2). If a hypersensitivity reaction occurs, dosing of the participant will be stopped (Section 7.1).

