7 DISCONTINUATION OF STUDY INTERVENTION AND PARTICIPANT DISCONTINUATION/WITHDRAWAL

7.1 Discontinuation of Study Intervention

It may be necessary for a participant to discontinue study intervention temporarily or permanently. An individual participant will discontinue study intervention (either temporarily or permanently) if any of the following occurs in the participant in question:

- 1 An AE that in the opinion of the investigator or the sponsor contraindicates dosing.
- 2 Clinical symptoms of spontaneous bleeding so that the PI judges further administration of study intervention should be paused or stopped.
 - (a) Providers should consider temporary or permanent discontinuation of study intervention in participants who:
 - (i) Develop a condition that requires the use of chronic therapeutic anticoagulation therapy.
 - (ii) Experience severe bleeding that is not readily explained by a reversible alternate etiology. All bleeding events should be treated and followed up according to local clinical practice. Study intervention may be resumed when the risk of bleeding is deemed low in the judgment of the investigator.
 - (b) Study intervention must be stopped in the event of severe thrombocytopenia (platelet count < 50000 platelets/ μ L) which does not resolve, or if after resolution the investigator thinks it is not appropriate to restart study intervention because it may put the participant at undue risk.
- 3 A generalized hypersensitivity reaction occurring which, in the opinion of the PI and/or the Medical Monitor, would warrant discontinuation.
- 4 After initial dosing, there exists a clinically significant safety issue based on information not known or not disclosed before randomization.
- 5 Participant non-compliance that, in the opinion of the investigator or sponsor, warrants withdrawal (eg, refusal or inability to adhere to scheduled visits).
- 6 Withdrawal of consent.

If study intervention is permanently discontinued, the participant will remain in the study to be evaluated for protocol-specified assessments including follow-up of any AEs unless consent is withdrawn from further study participation (Section 7.2) or the participant is lost to follow-up (Section 7.3).

Note that discontinuation from study intervention is NOT the same as a withdrawal from the study.

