8 STUDY ASSESSMENTS AND PROCEDURES

- Study procedures and their timing are summarized in the SoA (Section [1.3](#)). Protocol waivers or exemptions are not allowed.
- Immediate safety concerns should be discussed with the sponsor immediately upon occurrence or awareness to determine whether the participant should continue or discontinue study intervention.
- Adherence to the study design requirements, including those specified in the SoA, is essential and required for study conduct.
- An optional pre-screening visit to collect local laboratory values for hs-CRP and creatinine (for eGFR calculation) may occur upon completing the pre-screening informed consent within 42 days before signing the screening ICF (screening Visit 1). If randomization of participants with NT-proBNP < 125 pg/mL is capped, NT-proBNP (or BNP if NT-proBNP is not available) may also be collected during pre-screening.
- All screening evaluations must be completed and reviewed to confirm that potential participants meet all eligibility criteria. The investigator will maintain a screening log to record details of all participants screened and to confirm eligibility or record reasons for screening failure, as applicable.
- Procedures conducted as part of the participant’s routine clinical management and obtained before signing of the ICF may be used for screening or baseline purposes provided the procedures met the protocol-specified criteria and were performed within the time frame defined in the SoA.
- The maximum amount of blood collected from each participant over the duration of the study, including any extra assessments that may be required, will not exceed 630 mL. Repeat or unscheduled samples may be taken for safety reasons or if there are technical issues with the samples.

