8.2.5.3 Injection Site Reactions

Study participants will be monitored for injection site reactions. All injection site reactions will be recorded as AEs and further characterized.

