When making an assessment of causality, consider the following factors when deciding whether there is a ‘reasonable possibility’ that an AE may have been caused by the study intervention.

- Time Course. Exposure to study intervention. Has the participant actually received the study intervention? Did the AE occur in a reasonable temporal relationship to the administration of the study intervention?
- Consistency with known drug profile. Was the AE consistent with the previous knowledge of the study intervention (pharmacology and toxicology) or interventions of the same pharmacological class? Or could the AE be anticipated from its pharmacological properties?
- De-challenge experience. Did the AE resolve or improve on stopping or reducing the dose of the suspect drug?
- No alternative cause. The AE cannot be reasonably explained by another etiology such as the underlying disease, other drugs, other host or environmental factors.
- Re-challenge experience. Did the AE re-occur if the study intervention was reintroduced after having been stopped? The sponsor would not normally recommend or support a re-challenge.
- Laboratory tests. A specific laboratory investigation (if performed) has confirmed the relationship.

In difficult cases, other factors could be considered such as:

- Is this a recognized feature of overdose of the study intervention?
- Is there a known mechanism?

Causality of ‘related’ is made if following a review of the relevant data, there is evidence for a ‘reasonable possibility’ of a causal relationship for the individual case. The expression ‘reasonable possibility’ of a causal relationship is meant to convey, in general, that there are facts (evidence) or arguments to suggest a causal relationship.

The causality assessment is performed based on the available data including enough information to make an informed judgment. With no available facts or arguments to suggest a causal relationship, the event(s) will be assessed as ‘not related’.

Causal relationship in cases where the disease under study has deteriorated due to lack of effect should be classified as no reasonable possibility.

B 4 Study Intervention Error

For the purposes of this clinical study, a study intervention error is an unintended failure or mistake in the process for administering a study intervention that either causes harm to the participant or has the potential to cause harm to the participant.

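### Protocol Section 8.2.5.2 and Table 6 stop dosing after any hypersensitivity reaction, but Section 7.1, which Table 6 cites for this, does not contain that rule

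*Protocol*

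**What the plan says.** Three places in the protocol state a stop for hypersensitivity.

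- **Section 8.2.5.2:** "If a hypersensitivity reaction occurs, dosing of the participant will be stopped". The stop is not limited by severity or extent, and it is not left to anyone's judgment. The word *severe* appears in the preceding sentence, on clinical management, but not in the stopping sentence.
- **Section 2.3.1, Table 6**, under mitigation for hypersensitivity, anaphylaxis and immune complex disease: "If a hypersensitivity reaction occurs, dosing of the participant will be stopped (Section 7.1"). This is the same unqualified stop, and it names Section 7.1 as the source.
- **Section 7.1, criterion 3:** "A generalized hypersensitivity reaction occurring which, in the opinion of the PI and/or the Medical Monitor, would warrant discontinuation". This carries two conditions, extent and judgment.

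The lead-in to Section 7.1 is: "An individual participant will discontinue study intervention (either temporarily or permanently) if any of the following occurs". Criterion 1 of the same list is "An AE that in the opinion of the investigator or the sponsor contraindicates dosing". Criterion 4 covers a clinically significant safety issue that arises after initial dosing from information not available before randomization.

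Two other texts bear on re-dosing. Section 8 says that immediate safety concerns "should be discussed with the sponsor immediately upon occurrence or awareness to determine whether the participant should continue or discontinue study intervention". Appendix B 3, in its guide to judging causality, says: "The sponsor would not normally recommend or support a re-challenge".

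**The concern.** The stop is a stated safeguard against a risk that includes anaphylaxis and immune complex disease, in a biologic given for nine doses. Section 7.1 is the discontinuation section, so it is where staff would look when deciding whether to give the next dose. There they find a narrower, judgment-based criterion in place of the stop that Table 6 attributes to it.

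What is at stake is uneven handling of re-exposure across approximately 70 to 100 sites. Table 4 schedules the two-hour in-clinic observation only at Day 1 and Day 29, the first two doses. A participant re-dosed later would have no scheduled two-hour observation, so the rule on stopping carries more weight. Section 8 does not allow protocol waivers, so a site that re-dosed by using the discretion in criterion 3 would be out of line with Section 8.2.5.2.

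**Working it through.** There is no figure in the plan to reproduce and no formula to apply. The check sets the rules side by side.

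**Inputs.** The stopping sentences in Section 8.2.5.2 and Table 6, and the lead-in and criteria 1, 3 and 4 of Section 7.1. All are current body text, and none of the quoted sentences is redacted.

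**Step 1: what each text requires.** Divide reactions by whether they are generalized, and by whether someone entitled to judge under Section 7.1 decides that dosing should not go on. That gives 2 × 2 = 4 cases.

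| Reaction | Judged to warrant discontinuation or contraindicate dosing? | 8.2.5.2 and Table 6 | Section 7.1 |
|---|---|---|---|
| Generalized | Yes | Stop | Stop (criterion 3) |
| Generalized | No | Stop | No stop required by criterion 3 or 1 |
| Not generalized | Yes | Stop | Stop (criterion 1) |
| Not generalized | No | Stop | No stop required by criterion 3 or 1 |

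Section 8.2.5.2 and Table 6 require a stop in 4 of 4 cases. Criteria 1 and 3 of Section 7.1 require one in 2 of 4. These are counts of rule cases, not frequencies of reactions. The judgment column also merges two different tests: criterion 3 belongs to the PI and/or Medical Monitor, criterion 1 to the investigator or sponsor.

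**Step 2: can criterion 4 fill the gap?** In part. A clinically significant reaction that first appears on treatment arguably fits it, and it has no wording that makes it a matter of opinion. It would not reach a reaction that is not clinically significant, and it does not mention hypersensitivity.

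**Step 3: are the texts incompatible?** No. Section 7.1 lists triggers that are sufficient for discontinuation. Where none is met, it does not direct the site to continue. In all 4 cases a site that stops satisfies all three places.

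**Step 4: do they state the same rule?** No. If every reaction requires a stop, both conditions in criterion 3 have no function. The citation in Table 6 therefore points to a section that does not hold the rule.

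**Step 5: does a temporary reading of the stop resolve this?** No. The lead-in to Section 7.1 makes even temporary discontinuation depend on its criteria. Section 8.2.5.2 and Table 6 do not say whether the stop is temporary or permanent. Section 7.1 does give a resumption condition for severe bleeding, but none for hypersensitivity.

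**The case against.** The strongest case on the other side is that nothing unsafe is written. The explicit, repeated rule is the protective one. The same Table 6 cell refers readers to Section 8.2.5.2 for managing severe reactions, and that section states the unconditional stop under a heading about hypersensitivity. Section 8 calls for immediate discussion with the sponsor, and Appendix B 3 discourages re-challenge. Divergence between sites is a possibility, not something the documents show. All of this stands, and it keeps the severity low. It does not close the gap: the Section 8 text applies to immediate safety concerns, Appendix B 3 is causality guidance, and neither says which stopping rule governs.

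A reader might infer more than the documents support in three ways.

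- **That the sections directly contradict each other for some reactions.** They do not. Section 7.1 never tells a site to continue dosing, so stopping always complies.
- **That Section 7.1 requires a stop for generalized reactions alone.** It does not. Criterion 1 reaches any adverse event judged to contraindicate dosing, and criterion 4 arguably reaches a clinically significant new reaction.
- **That the texts should be aligned by turning the stop into a hold with resumption by the PI, exempting isolated injection site reactions.** That would loosen the stricter written safeguard, and its downside is re-exposure after a reaction. Section 8.2.5.3 gives no basis for the exemption. It says "All injection site reactions will be recorded as AEs and further characterized" and does not separate these reactions from hypersensitivity.

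**Conclusion.** The point holds as an inconsistency in a safety rule. Two of the three statements are unconditional. The third, in the section cited as the source, carries two conditions. A site that stops complies everywhere, but a site relying on Section 7.1 alone could re-dose after a reaction for which Table 6 promises a stop.

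Severity is low. No number of reactions is assumed, and no effect on the primary endpoint is claimed: Section 7.1 keeps participants who permanently discontinue in the study for assessment, and membership of the CTA analysis population does not depend on doses received. The conclusion rests on reading the stop in Section 8.2.5.2 and Table 6 as intended to apply to any reaction, as written. The documents do not settle whether the sponsor means it to be permanent.

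**What to change.** Make Section 7.1 carry the rule that Table 6 attributes to it.

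1. Change criterion 3 of Section 7.1 to *Any hypersensitivity reaction*, so that dosing is always stopped, temporarily or permanently, under the existing lead-in.
2. State there whether the stop is permanent. If resumption is ever allowed, require a documented decision by the PI and the Medical Monitor.
3. Add a cross-reference to Section 7.1 in Section 8.2.5.2.
4. Leave the stop in Section 8.2.5.2 and Table 6 as strong as it is now. Do not add an exemption for injection site reactions unless the sponsor confirms that it is intended.

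The cost is a few sentences in the next amendment, and a few more stopped or held doses than criterion 3 alone would require. Measured against Section 8.2.5.2 as it stands, no additional stops are created.
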